#### **Summary of Study Design:**

A multisite, randomized, double-blind, parallel, placebo-controlled trial with 4 study periods in patients who meet International Classification of Headache Disorders (ICHD) criteria for a diagnosis of migraine as confirmed during a prospective baseline period that demonstrates episodic frequency (4 to 14 migraine headache days per month).

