#### **Patient and Disease Characteristics**

- [1] Patients are 18 to 65 years of age (inclusive) at the time of screening.
- [2] Have a diagnosis of migraine as defined by International Headache Society (IHS) International Classification of Headache Disorders (ICHD)-3 beta guidelines (1.1 or 1.2) (ICHD-3 2013), with a history of migraine headaches of at least 1 year prior to Visit 1, and migraine onset prior to age 50.
- [3] Prior to Visit 1, have a history of 4 to 14 migraine headache days and at least 2 migraine attacks per month on average within the past 3 months.
- [4] From Visit 2 to Visit 3 (prospective baseline period), have a frequency of 4 to 14 migraine headache days and at least 2 migraine attacks (see definitions, Table CGAH.1). To avoid biased reporting, patients must not be told the number of migraine headache days on which study qualification is based.
- [5] From Visit 2 to Visit 3 (prospective baseline period), must achieve sufficient compliance with ePRO daily headache entries as demonstrated by completion of at least 80% of daily diary entries.

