## 6.2. Method of Treatment Assignment

Patients who meet all criteria for enrollment will be randomized to double-blind treatment at Visit 3. Assignment to treatment groups will be determined by a computer-generated random sequence using an interactive web-response system (IWRS). The IWRS will be used to assign double-blind investigational product to each patient. Site personnel will confirm that they have located the correctly assigned package by entering the confirmation number found on the package into the IWRS.

To achieve between-group comparability, the randomization will be stratified by country and baseline migraine frequency (<8 migraine headache days versus  $\ge8$  migraine headache days). To ensure an appropriate balance of low- and high-frequency migraine headache day patients, the sponsor will stop enrollment of low-frequency patients if the number exceeds an estimated 578.

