#### Schedule of Activities, Protocol I5Q-MC-CGAH (footnotes)

- a The eligibility period of the prospective baseline assessment will last from 30 to 40 days. Investigators and patients may have up to an additional 5 days to schedule their Visit 3 appointment (beyond the 40 days); however, eligibility will be based on the 30-40 day period.
- b Visit is to include a review of any spontaneously reported adverse events and collection of blood samples for immunogenicity, PK, and CGRP plasma.
- c Visit 9 and Visit 11 are laboratory visits (for PK and CGRP plasma) only. Adverse events are not intended to be collected at these visits because patients may be going to a different location for laboratory assessments. However, any spontaneously reported AEs at these lab visits should be reported on the AE page.
- d A neurological exam will be conducted at screening, Month 3 and Month 6 of treatment, as well as at the final visit of the follow-up period or early termination visit in order to assess for any signs of pre-existing or treatment-emergent neurological abnormalities such as stroke or other cerebrovascular events.
- Electrocardiograms (ECGs) will be performed at Visit 1, Visit 3, Visit 12, and Visit 14 or early termination. Note: The Visit 3 ECG should be collected prior to blood draws and dosing. Patients must be supine for approximately 5 to 10 minutes before ECG collection and remain supine but awake during ECG collection.
- f Vital signs will include body temperature, blood pressure and pulse. Blood pressure and pulse will be measured in triplicate in the sitting position and should be measured prior to blood draws. Blood pressure will be assessed by utilizing a calibrated machine.
- g Chemistry samples collected at Visit 3, Visit 7, Visit 12, and Visit 14 or early termination must be fasting. Fasting is defined as no food or drink, except water, for at least 8 hours prior to testing.
- h In the event of a positive urine leukocyte esterase result, a repeat urine sample will be collected and shipped to the central laboratory.
- i A positive urine test must be followed by a serum pregnancy test for confirmation.

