Q1. Yesterday, did you have a headache that lasted for thirty minutes or more?	Yes	Migraine if at least two migraine Criteria A's and at least one migraine Criteria B.
,	No ^a	
Q2. Enter the total number of hours you had a headache yesterday.	Range 1 to 24	If ≥1, the headache will be counted as a headache day.
Q3. Yesterday, what was the worst	Mild	
headache pain?	Moderate	Migraine Criteria A
	Severe	Migraine Criteria A
Q4. Yesterday, was the headache	Yes	Migraine Criteria A
throbbing or pounding?	No	
Q5. Yesterday, was the headache just on	Yes	Migraine Criteria A
the right or left side of your head?	No	
Q6. Yesterday, was the headache made	Yes	Migraine Criteria A
worse by your usual daily activity	No	
Q7. Yesterday, did the headache come	Yes	Migraine Criteria B
with sensitivity to light and sound?	No	
Q8. Yesterday, did you feel sick to the	Yes	Migraine Criteria B
stomach or throw-up with the headache?	No	
Q9. Yesterday, did you have your	Yes	
menstrual period (if female)?	No	
Q10. Yesterday, did you take any medicine for your headache?	Yes	Medication will only count as headache medication on a day a headache occurred.
, and the second	No	·
Q11. Yesterday, did you take any	Yes	
medication for pain other than headache?	No	
Q12. Yesterday, did you experience aura?	Yes	
	No	
Q13. Yesterday, did you experience any	Yes	
warning symptoms other than aura (prodrome symptoms) that a migraine was coming?	No No	

^a If "No" is answered for Q1, then the patients will skip Q2 - Q6, only answer questions Q7 - Q13.

Primary Measure: The Number of Monthly Migraine Headache Days

The primary measure is the number of monthly migraine headache days. A migraine headache day is defined as a calendar day on which a **migraine or probable migraine** occurs.

The primary measure of the number of monthly migraine headache days will be summarized from the daily ePRO data for each patient in that period (including 30 days of daily data from the baseline period prior to randomization, 6 months of daily data during the treatment phase, and 4 months of daily data during the post-treatment phase).

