Appendix Table 1. Description of Important Protocol Deviations

Category	Subcategory	Study-specific	Source	Methods of Identification
Informed Consent	Informed consent not obtained	Initial ICF date is missing or is after (Visit 1 Date or Visit 1 lab date)	Programmable – Stats	For all patients, if Initial ICF date is missing or after (Visit 1 date or Visit 1 lab date).
	Improper Consent	ICF not signed prior to initiation of protocol procedures	Non-Programmable- Monitor identified	Or determined by study team
Eligibility	Inclusion/ Exclusion	Age <18 or >65 years old at study entry	Non-Programmable- Monitor identified	
		BMI ≥40 at baseline	Programmable - Stats	
		Number of migraine headache days <4 or >14 at baseline	Programmable - Stats	Number of Normalized migraine headache days <4 or >14 at baseline
		Number of migraine attack <2 at baseline	Programmable - Stats	Number of Normalized migraine headache attack <2 at baseline
		Baseline ePRO compliance <80%	Programmable - Stats	
		Female patients who have a positive serum pregnancy test prior to randomization visit	Programmable – Stats	For randomized female patients, if serum pregnancy test is positive any time prior to Visit 3
		Female patients who have a positive or no serum pregnancy test prior to randomization visit	Non-Programmable- Monitor identified	

Category	Subcategory	Study-specific	Source	Methods of Identification
Eligibility	Eligibility Inclusion/ Exclusion	Insufficient Washout of prohibited migraine preventive medication for at least 30 days prior to Visit 2	Programmable - Stats	Patients must have discontinued such treatment at least 30 days prior to Visit 2.
		Insufficient Washout of Botulinum toxin A and B at least 4 months prior to Visit 2	Non-Programmable- Study Team identified	 Stats will create the list of patients meet this IPD criteria. Among those, the true IPDs will be manually added into non-programmable excel sheet.
		With suicidal ideation (Q4 or Q5) within past month of visit 1.	Programmable - Stats	Randomized patients with answer "yes" for C-SSRS suicidal ideation Q4 or Q5 occurred within past 1 month of Visit 1.
		Positive or No urine drug screen prior to randomization	Programmable - Stats	For randomized patients if prior to Visit 3, a patient has a positive UDS result and a repeated UDS not done or last repeat UDS is positive or UDS never collected.

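### Protocol and SAP do not use one common basis (window count or count per 30 days) for baseline eligibility, the frequency stratum and the deviation flags

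*SAP*

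**What the plan says.** - **Eligibility.** Criterion [4] in Protocol Section 5.1 reads: "From Visit 2 to Visit 3 (prospective baseline period), have a frequency of 4 to 14 migraine headache days and at least 2 migraine attacks". No time unit is given beyond the window itself. Criterion [3], on the history before Visit 1, uses the same numbers but makes them monthly averages. Appendix 2, footnote a, fixes the window: "eligibility will be based on the 30-40 day period". Visit 3 itself may fall up to 5 days later. Criterion [5] requires "completion of at least 80% of daily diary entries". The synopsis describes a baseline that "demonstrates episodic frequency (4 to 14 migraine headache days per month"; that rate covers headache days and says nothing of attacks.
- **Stratum.** Protocol Section 6.2: "the randomization will be stratified by country and baseline migraine frequency", cut at 8 days, with no time unit. SAP Section 5.3 has the same cut, but per 30 days. Both cap low-frequency enrolment at 578 (the protocol calls this an estimate).
- **Scaling.** SAP Section 5.4.1 multiplies headache days by 30/x, where x is the number of diary days that are not missing. It extends the 30-day adjustment to a list of diary measures that includes attacks. SAP Section 5.5.1.2 exempts attacks from the missing-diary approach and fills their missing days by LOCF.
- **Flags.** SAP Appendix Table 1 lists as important eligibility deviations a normalised day count below 4 or above 14, and "Number of Normalized migraine headache attack <2 at baseline". It also lists any disagreement between the IWRS category and the diary-derived category, under the label of an IWRS entry error.

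Sites are told at the end of baseline whether a patient qualifies (Protocol Section 4.1, Study Period II). Neither document says which count that check, or the IWRS, uses.

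**The concern.** A deviation flag should find patients who broke the entry rule. Here the rule is written on a window of variable length and the flag on a 30-day scale, so a patient can satisfy one and fail the other. The deviation table would then show enrolment failures that are only a difference of definition.

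The same gap affects the stratum. The <8/≥8 category governs the stratified randomisation and the 578 cap. It is a covariate in efficacy models other than those for migraine headache days and response rates (SAP Section 5.5.1.1; PGI-S, a key secondary measure, is one of them). It also stratifies the log-rank tests (Section 5.5.10.3) and defines a subgroup (Section 5.5.13). If the IWRS and the analysis use different counts, the disagreement is reported as a data-entry fault.

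The deviation table was added in SAP Version 4, approved in April 2017. The SAP's revision history places interim analysis #1 in October 2016, so patients had been enrolled under criterion [4] before these flags were written.

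**Working it through.** The plan gives no count of flagged or re-stratified patients, so there is no figure of its own to reproduce. The one related number is the cap: 578/825 = 70%.

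**Inputs.** Window L = 30 to 40 days (Protocol Appendix 2, footnote a). Limits of 4 to 14 days and at least 2 attacks (criterion [4]). Diary completion of at least 80% (criterion [5]). Scaling of 30/x (SAP Section 5.4.1).

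**Step 1: full diary.** Scaled value = count × 30/L.

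| Window (days) | 2 attacks | 3 attacks | 4 days | 5 days | Day counts of 8 or more that scale below 8 |
|---|---|---|---|---|---|
| 30 | 2.00 | 3.00 | 4.00 | 5.00 | none |
| 31 | 1.94 | 2.90 | 3.87 | 4.84 | 8 |
| 35 | 1.71 | 2.57 | 3.43 | 4.29 | 8, 9 |
| 38 | 1.58 | 2.37 | 3.16 | 3.95 | 8, 9, 10 |
| 40 | 1.50 | 2.25 | 3.00 | 3.75 | 8, 9, 10 |

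Exactly 2 attacks is flagged in every window over 30 days; 3 attacks never is. Four headache days is flagged from 31 days on, and five from 38. In a 40-day window, 8, 9 and 10 days become 6.0, 6.75 and 7.5, the other stratum.

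The attack column divides by calendar days, which fits an LOCF-filled diary. If attacks were divided by non-missing days, the flag would need more than 30 completed days. A 40-day window at 80% has 32, and 2 × 30/32 = 1.88 is still flagged. A 35-day window with 30 completed days gives 2.00 and is not.

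**Step 2: the other direction.** Fifteen to 18 days in 40 scale to 15 × 30/40 = 11.25 up to 18 × 30/40 = 13.5. They lie inside 4 to 14 per 30 days but fail an unscaled limit of 14.

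**Step 3: missing entries.** With 24 diary days in a 30-day window (80%), 14 days scale to 14 × 30/24 = 17.5, above the limit, and 7 days to 7 × 30/24 = 8.75, up a stratum. SAP Section 5.4.1 is unclear on whether a 30-day period with gaps is scaled: its trigger is a period that is not 30 days, but its divisor is non-missing days.

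**Step 4: how many patients.** The documents give neither the distribution of window lengths nor the variation in baseline counts. A diary simulation assumed a mean of 8 to 9 and SD of 3 to 4 migraine headache days per 30 days, day-to-day persistence of 0.2 to 0.4 and completion of 85 to 100%, with eligibility and stratum both set on unscaled counts:

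| Windows | Eligible patients flagged | Stratum differs |
|---|---|---|
| all 30 days | 2 to 7% | 0.2 to 3% |
| mixed, 30 to 40 days | 6 to 15% | 8 to 17% |
| all 40 days | 8 to 18% | 24 to 31% |

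For mixed windows, 8 to 17% of 825 is 66 to 140 patients. A simpler model without missing entries (mean 7 or 9, SD 3) gives 21 to 23% for windows spread over 30 to 40 days. The result is driven by the assumptions. If the eligibility check and IWRS used the SAP's normalised values, mismatches from this source are zero.

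**The case against.** The strongest reply is that there is one rule, with its unit left out in places. The synopsis gives the day range per month for this same baseline, criterion [4] speaks of a frequency, criterion [3] puts both days and attacks per month, and Protocol Section 9.3.2 summarises baseline measures per 30 days. On that view the SAP only supplies the missing unit.

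Part of this stands. A reader might infer that the protocol prescribes raw counts; it never says so, and for headache days the monthly reading is available. It does not settle attacks. No monthly unit is attached to attacks for the prospective period, and criterion [4] drops the unit that criterion [3] carries. Reading the attack limit per 30 days would turn at least 2 into at least 3 in any window over 30 days, which the protocol nowhere states.

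Three further inferences should be resisted.

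- *Many patients change stratum.* This needs an IWRS that used unscaled counts, which neither document says.
- *A third baseline window.* SAP Section 5.4.1 mentions "including 30 days of daily data from the baseline period prior to randomization". The same section defines a month as 30 days normalised from the visit interval and gives the 30/x rule, which explains the phrase.
- *The main result is at risk.* The primary MMRM and the response-rate models use continuous baseline migraine headache days. Deviations are only tabulated and listed (SAP Section 5.5.3), and no per-protocol set is defined (Section 5.5.1.4). The stratum is assigned before randomisation, so misclassification does not bias the treatment comparison.

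**Conclusion.** The point holds as an inconsistency between a stated rule and its stated check. Taken as written, criterion [4] admits patients whom the SAP then lists as important eligibility deviations. The certain cases are exactly 2 attacks in a window over 30 days (with a complete diary or a calendar-day divisor) and 4 headache days with a full diary in such a window. The protocol and SAP also state the stratum on different terms. Whether any patient's stratum actually differs depends on the unstated IWRS count, and the number is unknown; the simulated shares, from 0.2 to 3% up to 24 to 31%, show only how strongly it depends on window length and completion.

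The harm is to the deviation listing, to the description of who was eligible, and possibly to the category used in secondary models, log-rank strata, one subgroup and the cap. The primary analysis is not affected. The correction is cheap and worth making.

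**What to change.** Reconcile Protocol Section 5.1 criterion [4], Section 6.2 and Appendix 2 footnote a with SAP Sections 5.3, 5.4.1 and 5.5.1.2 and Appendix Table 1:

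1. State the window, and the day and attack counts, that the eligibility check and the IWRS actually used.
2. Write the <8/≥8 stratum on that same basis in Protocol Section 6.2 and the SAP.
3. Program the day, attack and stratum deviation flags on that same count.
4. Test the attack flag on the attack count that eligibility used. Do not multiply the LOCF-filled attack count by 30 over non-missing diary days: the fill has already dealt with the missing days, so that would correct for them twice.

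Either basis, used throughout, removes mismatches from this source. Moving criterion [4] to a 30-day scale would change who qualifies on attacks, so it is more than a wording change and should be a deliberate choice.

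Cost: a few lines of text, reprogrammed flags and one check of the IWRS against the diary data.
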